7.9 Expected time and duration of the study

The study is expected to be completed in 12 months, divided as follows:

- **Months 1-2:** Ethical approval, recruitment of research assistants
- **Months 3-8:** Data collection (patient interviews, medical record review).
- **Months 9-10:** Data entry and analysis.
- **Months 11-12:** Report writing, dissemination of results, and publication

7.10 Tools and techniques for data collection

- Tools:

Questionnaire

The questionnaire is composed of six simple-to-complete sections.

Section 1:

- Patients provide essential contextual information about the medicines they are taking, when they are administered each day, and their understanding of why they are taking them.
- This helps clinicians compare a patient's actual medication usage with documented clinical records and uncover any medication changes since discharge.

Subsequent sections (Section 2-6):

- These sections use Likert scales instead of binary yes/no responses, which improves the quality of information gathered.
- For example, it allows the assessment of the frequency of non-adherence behaviors rather than just detecting non-adherence.

Section 2:

- Explores overall understanding and satisfaction with medicines.
- Patients respond to four statements regarding their understanding of why their medicines were prescribed and how well they think they are working, using a four-point Likert scale (strongly agree, agree, disagree, strongly disagree).

Sections 3–5:

- Assess specific modifiable barriers to adherence, using the same four-point Likert scale as section 2.
- A free-text box allows patients to specify which medicines their concerns involve.

Section 3:

- Explores three areas of anxiety about medicines (e.g., concerns about medicines causing more harm than good or feeling there are too many medicines).

Section 4:

- Examines four practical concerns associated with medicine-taking (e.g., difficulties with swallowing pills or obtaining repeat prescriptions).

Section 5:

- Assesses three issues related to fitting medicines into the patient's daily routine (e.g., forgetfulness or inconvenience).
- These issues are linked to non-adherence and can potentially be addressed in clinical practice.

Section 6:

- Focuses on adherence to each individual secondary prevention medication (SPM) over the past month.
- It uses a modified version of the SQ tool and a five-point Likert scale.
- Patients are considered non-adherent if they select any answer other than 'all of the time' for any SPM.

[figure not shown]
Technique:

- A relevant questionnaire will be developed and distributed to our research team. They will visit cardiology outpatient department (OPD) as well as in the cardiology ward in Manmohan

Cardiothoracic Vascular and Transplant Centre to administer and fill the questionnaire, asking patients who meet the research criteria the necessary questions.

- Prior to participation, participants will receive comprehensive information regarding the study's objectives, procedures, and potential risks and benefits. They will be assured that their personal information will remain confidential and solely utilized for research purposes.
- Participants are expected to provide truthful and accurate responses to all study inquiries and protocols.
- The questionnaire will be individually distributed to each participant.

7.13 A graphic outline of the study design and procedures using a flow diagram including the timing of assessments.

8. Plan for data management and statistical analysis

- Information on how the data will be managed (data handling and coding for computer analysis, monitoring and verification).
- Procedures for accounting for any missing or spurious data etc.
- The statistical methods and tests proposed to be used for the analysis of data.
- For projects involving qualitative approaches, specify in sufficient detail how the data will be analyzed.

9. Biases

- Selection Bias: The adherence behaviors of OPD patients may differ significantly from those of re-hospitalized patients. Re-hospitalized patients might have more severe conditions, leading to differences in adherence patterns. This could introduce bias in comparing adherence rates across both groups.
- Survivor Bias: Re-hospitalized patients represent those who have survived a second cardiac event. This excludes patients who may have suffered more severe outcomes or death, potentially skewing the findings.

- **Self-Reported Data:** The reliance on patient self-reports for adherence may introduce recall bias or social desirability bias, where patients overestimate their adherence to appear compliant.

10. Limitations of the study

- **Heterogeneity of Patient Conditions:** Re-hospitalized patients might have more complex medical histories or complications, while OPD patients might represent a more stable cohort. This could lead to difficulties in interpreting results uniformly across both groups.
- **Single-Centre Study:** Conducting the study in one tertiary care hospital limits the generalizability of the findings to other settings, such as rural or private healthcare facilities.
- **Cross-Sectional Design:** The study captures adherence at a single point in time, making it difficult to assess changes in adherence over time or the long-term effects of non-adherence.
- **Incomplete Records:** Excluding patients with incomplete medical records may result in the loss of potentially valuable data, especially if those patients differ systematically from others.
- **Confounding Factors:** Factors like access to healthcare, comorbidities, or socio-economic conditions may influence both adherence and re-hospitalization but might be difficult to fully account for in the analysis.

11. Safety considerations

This study on medication adherence post-acute coronary syndrome (ACS) prioritizes participant safety by ensuring confidentiality, obtaining informed consent, and designing the questionnaire to minimize discomfort. Participants can skip any questions that may cause unease, and those facing adherence challenges will receive information on local support resources. Though risks are minimal, any adverse events will be recorded, with participants advised to seek medical help if necessary. The study follows ethical guidelines approved by our institution's ethics board to safeguard participant well-being throughout the research.

12. Plan for supervision and monitoring

- **Developing the Plan:** We will outline responsibilities of the research team and external supervisors, including key activities and milestones for data collection, follow-ups, and quality checks.
- **Communication Channels:** We will establish regular meetings, email, and phone updates to maintain clear communication and address study progress or challenges in real time.
- **Regular Meetings:** We will schedule weekly and monthly meetings with the research team and supervisors to review progress, resolve issues, and ensure adherence to the timeline.
- **Data Quality Monitoring:** We will conduct regular checks on data accuracy and consistency, addressing errors immediately to maintain the integrity of the data.
- **Progress Review:** We will continuously track recruitment, data collection, and adherence to timelines, ensuring the study remains on schedule and goals are met.

- **Issue Resolution:** We will address any arising issues promptly by adjusting protocols or consulting external supervisors, ensuring the study remains on track.

13. Expected outcome of the research

- **Adherence Rates:** We will determine the level of adherence to secondary prevention medications among patients re-hospitalized after ACS in Nepal.
- **Factors Influencing Non-Adherence:** We will identify key factors contributing to non-adherence, such as socio-economic barriers, patient knowledge, and healthcare system challenges.
- **Targeted Interventions:** The findings will inform targeted interventions to improve medication adherence and reduce re-hospitalization rates.
- **Policy Insights:** We will provide valuable insights for healthcare policy improvements in post-ACS care, helping enhance long-term cardiac outcomes in Nepal.
- **Patient Education:** The study will highlight the need for increased patient education on the importance of medication adherence.

14. Plan for dissemination of research results

- **Writing a research report:** We plan to create a detailed research report outlining the study's objectives, methodology, results, and conclusions, with an emphasis on findings related to medication adherence following acute coronary syndrome (ACS).
- **Publishing the research report:** We intend to submit the research report for publication in a reputable peer-reviewed journal focusing on cardiology or public health to ensure it reaches a scientific audience interested in ACS management and adherence studies.
- **Sharing the research report with the research team:** We will distribute the report to all members of the research team, including collaborators and supervisors, to keep everyone informed of the outcomes and enable them to incorporate findings into their ongoing work.
- **Sharing the research report with relevant stakeholders:** We plan to disseminate the report to key stakeholders such as cardiology departments to support improvements in patient care and policy development.
- **Presenting the research findings:** We will present our findings at national and international cardiology or public health conferences, allowing us to share insights with a broader audience of healthcare professionals and researchers.

15. Plan for utilization of the research finding

- **Reviewing the research findings:** We will review the research findings thoroughly to understand the implications for patient care and the management of secondary prevention adherence following acute coronary syndrome (ACS).
- **Sharing the research findings with relevant stakeholders:** We plan to share our findings with relevant stakeholders, such as cardiologists, healthcare providers, hospital administrators, policymakers, and patient advocacy groups, to promote awareness and encourage support for improved adherence strategies.

- **Developing recommendations for practice and policy:** Based on the research results, we will develop targeted recommendations for clinical practice and policy aimed at enhancing medication adherence and follow-up care among ACS patients, with a focus on feasible strategies for Nepal's healthcare context.
- **Communicating the recommendations:** We will communicate these recommendations to relevant stakeholders through presentations, workshops, and written materials such as policy briefs and practice guidelines, helping translate our findings into actionable steps.
- **Implementing the recommendations:** We plan to collaborate with healthcare providers and institutions to incorporate our recommendations into clinical settings, ensuring that ACS patients receive comprehensive adherence support and education.
- **Monitoring the implementation of the recommendations:** We will monitor the adoption and effectiveness of the recommendations by gathering feedback from healthcare providers and assessing adherence improvement among ACS patients over time.
- **Evaluating the impact of the recommendations:** We will evaluate the impact of our recommendations on adherence outcomes, healthcare utilization, and patient health, using this evaluation to inform future research and to optimize secondary prevention efforts in ACS care.

16. Work plan

Total duration of study: 12 months

Timeline: Gantt chart

- **August 2024**
 - Planning and discussion of the research title
- **October 2024 to November 2024**
 - Literature Review and Questionnaire Development
- **December 2024 to June 2025**
 - Contacting participants and data collection
 - All participants will complete a questionnaire.
- **August 2025**
 - Data analysis-The data collected from the assessment questionnaire will be analyzed.

17. Ethical issues and considerations regarding human participants

- Are human participants required in this research? If yes, offer justification.

Yes, human participants are required in this research. The study aims to assess adherence to secondary prevention medications among patients who have experienced Acute Coronary Syndrome (ACS). This research requires direct data collection from individuals who have been prescribed such medications to understand their adherence patterns, factors influencing adherence, and potential barriers. The insights gained from these participants will contribute to improving post-ACS care in Nepal and reducing the risk of recurrent cardiac events.

- Clearly indicate the participant's responsibilities in the research. What is expected of the research participants during the research?
 - **Providing informed consent:** Participants will be fully informed about the purpose, procedures, and potential risks and benefits of the study before deciding whether or not to participate.

- **Completing study procedures:** Participants should be willing to fill out the questionnaire.
- **Protecting their own privacy:** Participants should be aware that their personal information will be kept confidential and only used for the purposes of the study
 - **Protecting the confidentiality of others:** Participants should not disclose any information about other participants or the study to anyone outside of the research team.
 - **Providing honest and accurate responses:** Participants should provide honest and accurate responses to all study questions and procedures.

- Are vulnerable members of the population required for this research? If yes, offer justification.

No

- Are there any risks to the involved participants? If yes, identify clearly what are the expected risks for the human participants in the research and provide a justification for these risks.

No

- Are there any benefits to participants? If yes, identify clearly what are the expected benefits for the participants.

Indirect Benefits to Healthcare: Participants contribute to research that aims to improve post-ACS care and enhance medication adherence strategies, potentially benefiting future patients.

Personal Satisfaction: Patients may feel a sense of fulfillment by contributing to research that could improve public health and the care of other ACS patients.

Awareness and Self-reflection: By participating, patients may gain a better understanding of the importance of medication adherence, which could positively influence their own adherence behaviors.

18. Informed consent

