In summary, this study is essential for understanding why patients in Nepal fail to adhere to life-saving medications post-ACS and what can be done to mitigate this problem, ultimately improving patient care and reducing the burden on the healthcare system.

5. Objectives

a. General objectives:

To assess the level of adherence to prescribed secondary prevention medications and identify the factors influencing adherence among patients with Acute Coronary Syndrome (ACS) in Nepal.

b. Specific objectives:

- **To assess the level of adherence to secondary prevention medications (SPMs) among patients discharged after an Acute Coronary Syndrome (ACS) event, including antiplatelets, statins, beta-blockers, and ACE inhibitors/ARBs.**
- **To explore the influence of patient demographic factors** (such as age, gender, education level, occupation, and place of residence) and clinical characteristics (type of ACS, comorbidities) on medication adherence.
- **To identify patient-reported barriers to medication adherence**, including concerns about medication side effects, pill burden, practical issues with medication administration, and difficulties in integrating medications into daily routines.
- **To evaluate the relationship between medication adherence and clinical outcomes**, such as recurrent cardiac events, rehospitalization.

6. Research questions/hypothesis

- What is the level of adherence to secondary prevention medications among Acute Coronary Syndrome (ACS) patients in Nepal, and what demographic, clinical, and patient-reported factors influence this adherence and its associated clinical outcomes?

7. Research design and Methodology

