7.8 Study variables

Dependent Variable:

- **Adherence to Secondary Prevention Medications (SPMs):** This includes adherence levels to specific medications such as antiplatelets, statins, beta-blockers, and ACE inhibitors/ARBs, measured through MYMEDS questionnaire.

Independent Variables:

1. Demographic Factors:

- Age
- Gender
- Education Level
- Occupation
- Place of Residence (Rural vs. Urban)
- Monthly Income

2. Clinical Characteristics:

- Type of Acute Coronary Syndrome (e.g., STEMI, NSTEMI, Unstable Angina)
- Comorbidities (e.g., Hypertension, Diabetes Mellitus, Dyslipidemia, Chronic Kidney Disease)

3. Patient-Reported Factors:

- Concerns about medication side effects
- Pill burden (number of medications)
- Practical issues with medication administration (e.g., difficulties opening bottles)
- Difficulty integrating medications into daily routines

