 - 4. Semi-skilled worker**
 - Factory or workshop laborer, laboratory or library attendant, car cleaner

5. Unskilled worker

- Watchman, peon, domestic servant, rickshaw puller

6. Unemployed

9. **Family Monthly Income (NPR):** _____

- $\geq 97,451$
- 48,751–97,450
- 36,551–48,750
- 24,351–36,550
- 14,551–24,350
- 4,851–14,550
- $\leq 4,850$

10. **Place of Residence:**

- [] Rural
- [] Urban

11. **Distance from Healthcare Facility:** _____ (km)

Section 2: Clinical Information

1. **Type of ACS:**

- [] ST-Elevation Myocardial Infarction (STEMI)
- [] Non-ST-Elevation Myocardial Infarction (NSTEMI)
- [] Unstable Angina

2. **Date of ACS Diagnosis:** _____

3. **Treatment Received:**

- [] Percutaneous Coronary Intervention (PCI)
- [] Coronary Artery Bypass Grafting (CABG)
- [] Medical Management Only

4. **Comorbidities:**

- [] Hypertension
- [] Diabetes Mellitus
- [] Dyslipidemia
- [] Chronic Kidney Disease
- [] Stroke
- [] Peripheral Arterial Disease
- [] Others (Specify): _____

Section 3: Assessment of Adherence**MYMEDS Questionnaire****Section 1: Current Medicines**

Serial Number	Name of Medicines	Administration Time (Morning/Afternoon/Evening/Night)	Reason for Taking Medicine
1	Antiplatelets	_____	_____
2	Statins	_____	_____
3	Beta-blockers	_____	_____
4	ACE inhibitors/ARBs	_____	_____
5	Others (Loop diuretics, Nitrates, specify)	_____	_____

Section Number	Statement	Strongly agree	Agree	Disagree	Strongly disagree
Section 2: Understanding and satisfaction with medicines	a. I fully understand my heart medicines and why they were prescribed.				
	b. My heart medicines seem to be working for me.				
	c. I feel convinced of the importance of all my heart medicines.				
	d. At least occasionally, I need to alter my medicines on my own to make them work or meet my expectations.				

Section 3: Concerns about medicines	a. I worry that one or more of my medicines will do me more harm than good.				
	b. I feel concerned about being prescribed too many medicines.				
	c. I sometimes alter my medicines by cutting back or stopping taking them. (e.g. due to feeling worse, getting worried or for any other reason)				
Section 4: Practical issues that may be a barrier to adherence	a. I have difficulties or problems opening the medicine bottles or blister packs and would like a solution or an alternative.				
	b. I have difficulties or problems swallowing my medicine(s) and would like a solution or an alternative.				

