	c. I have difficulties or problems getting my repeat prescriptions and would like help ordering them from my GP or pharmacy.				
	d. I have difficulties or problems reading the label on the medicines bottle or box and would like a solution or alternative.				

Section 5: Fitting medicines into daily routine	a. I sometimes forget to take my heart medicines.				
	b. I am finding it difficult to fit one or more of my heart medicines into my daily routine.				
	c. I feel inconvenienced/bothered about sticking to all my heart medicines.				

Section 6: Adherence to Individual SPMs

For each of your prescribed medicines (SPMs), please indicate how often you have taken them as prescribed in the PAST MONTH:

Medication	All of the Time	Nearly All of the Time	Most of the Time	About Half the Time	Less than Half the Time
Aspirin					
ACE Inhibitor (e.g. Ramipril, Lisinopril,)					
Beta Blocker (e.g. Acebutalol)					
Medication 4 Statin (e.g. Simvastatin)					
ARIIA (e.g. Candesartan)					

Section 4: Clinical Outcomes

1. **Have you experienced any of the following since discharge?** (Check all that apply)
 - Recurrent chest pain
 - Rehospitalization for cardiac issues
 - Stroke
 - Heart failure symptoms
 - No major events
2. **Follow-up with healthcare provider since discharge:**
 - Yes
 - No
 - If Yes, how many visits: _____

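### The MYMEDS Section 6 grid rates antiplatelets through an aspirin row alone, although objective 1 and the dependent variable name the antiplatelet class

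*Combined protocol and SAP*

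**What the plan says.** - **Section 5b, first specific objective:** adherence to SPMs after discharge, "including antiplatelets, statins, beta-blockers, and ACE inhibitors/ARBs".
- **Section 7.8, dependent variable:** "adherence levels to specific medications such as antiplatelets, statins, beta-blockers, and ACE inhibitors/ARBs, measured through MYMEDS questionnaire".
- **Section 7.10, MYMEDS Section 6:** adherence is assessed for each individual SPM over the past month and scored by the rule "Patients are considered non-adherent if they select any answer other than 'all of the time' for any SPM".
- **Annex 1, MYMEDS Section 6 grid:** the stem asks how often each prescribed SPM was taken. Five rows follow: aspirin, ACE inhibitor, beta blocker, statin and ARIIA. The last four are class labels with example drugs, for instance "ACE Inhibitor (e.g. Ramipril, Lisinopril" and "Beta Blocker (e.g. Acebutalol". The text shows no row for another antiplatelet, no general row for other drugs, no blank row and no not-prescribed option.
- **Annex 1, MYMEDS Section 1:** antiplatelets appear as a class and there is a row for other medicines. The columns are the medicine, "Administration Time (Morning/Afternoon/Evening/Night" and the reason for taking it. None records how often it was taken.

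**The concern.** The objective promises a class-level result for antiplatelets, while the grid that would supply it names one drug. Two results are affected.

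The first is the antiplatelet-specific level. A patient on aspirin and a second antiplatelet is rated on aspirin only. A patient whose only antiplatelet is not aspirin has no antiplatelet rating at all. The figure reported for the class would describe aspirin.

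The second is the overall adherent proportion, which is also the outcome for the analysis of influencing factors. The any-drug rule can act only on rows that are rated. A patient who takes every listed drug faithfully but misses an unlisted antiplatelet is scored adherent.

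**Working it through.** **1. Objective against grid**

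| Class in objective 1 and 7.8 | Row(s) in the Section 6 grid | Whole class covered? |
|---|---|---|
| Antiplatelets | Aspirin | No: one drug |
| Statins | Statin, with example | Yes |
| Beta-blockers | Beta blocker, with example | Yes |
| ACE inhibitors/ARBs | ACE inhibitor; ARIIA, each with examples | Yes, in two rows |

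That is five rows: one for antiplatelets (aspirin), none for any other antiplatelet, and none for other drugs.

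**2. What the scoring rule does with this grid, completed as printed**

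- Aspirin plus another antiplatelet, only the other one missed: every listed row reads all of the time, so the patient is scored adherent.
- Non-aspirin antiplatelet only: no antiplatelet rating. The aspirin row is either left blank or given an answer that has no meaning.
- In the second case, if the aspirin row is marked low because the drug is not taken, the rule makes the patient non-adherent whatever was done with the prescribed drugs. If the patient is instead dropped for a missing answer, the denominator changes.

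The first case overstates adherence. The low mark understates it. Dropping a patient who is in fact adherent also lowers the proportion.

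**3. Yardstick from the plan**

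Section 7.6 uses p = 0.925 and d = 0.05: 1.96² × 0.925 × 0.075 / 0.05² = 106.60, against the stated 106.39, taken as 106. Then 106 × 1.10 = 116.6, stated as 117. (The terms printed in that line of 7.6, 0.924 and 1 − 0.817, do not give this result. That is a separate matter.) Only the sample sizes and the 5-point margin are used below.

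**4. Illustrative size (assumptions, not document figures)**

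Let s be the share of participants on a non-aspirin antiplatelet, and m the share of those who would be scored non-adherent on that drug alone. Overstatement from the missing row = s × m.

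| s | m | s × m (points) | Patients of 106 | Patients of 117 |
|---|---|---|---|---|
| 5% | 5% | 0.25 | 0.3 | 0.3 |
| 25% | 5% | 1.25 | 1.3 | 1.5 |
| 50% | 5% | 2.5 | 2.7 | 2.9 |
| 50% | 10% | 5.0 | 5.3 | 5.9 |

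None of these exceeds the planned 5-point margin; the last only reaches it. That last row is also demanding. If true adherence were the plan's 92.5%, 106 × 0.075 = 7.95 patients would be non-adherent, and 5.3 / 7.95 = 67% of them would have to be missing the unlisted drug and nothing else.

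**5. The sign is not fixed**

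Let a be the share not prescribed aspirin, and e the share of those who are adherent to all their prescribed drugs but marked low on the aspirin row. Net overstatement = s × m − a × e. With s = 25%, m = 5%, a = 10% and e = 20% (again assumptions), 1.25 − 2.0 = −0.75 points, an understatement.

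**The case against.** The strongest reply is that the form does ask about the other drugs. The grid stem refers to each prescribed SPM, 7.10 describes Section 6 in the same terms, and 7.5 has the researcher ask every question and complete the form. A careful interviewer could write in a second antiplatelet. This stands in part: it would be wrong to say that nothing directs rating of another drug. But there is no printed line for the answer and no procedure for adding one, so practice could vary between interviewers. Section 7.1 also allows online administration.

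It can also be said that the annex may not be the final form. Section 7.10 speaks of a questionnaire still to be developed, the statin row carries a leftover template label, a figure in 7.10 is not shown, and the free-text box that 7.10 describes for Sections 3–5 is not visible in the annex text. That lowers certainty about the form used in the field. The annex grid nevertheless reads as complete, and it is the form the protocol presents.

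A reader might infer that the bias can only be upward, because adding a row under an any-drug rule can only add non-adherent patients. That is true of the row in isolation. It does not hold for the form as a whole, which has no not-prescribed option.

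A reader might also infer a serious loss to the factor analysis: at 92.5% adherence, one hidden patient is 1 / 7.95 = 13% of the non-adherent group. But 92.5% comes from a different scale (7.6), and the Introduction cites adherence below 50% by 12 months. At 50%, one hidden patient is 1 / 53 = 1.9%. The documents do not support the larger figure alone.

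**Conclusion.** The mismatch between objective and grid follows from the text of the annex. Completed as printed, the grid yields an aspirin result where the objective promises an antiplatelet result, whatever the prescribing mix. A patient who misses only another antiplatelet is scored adherent.

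The effect on the overall proportion is of unknown size. The documents give neither the share on a non-aspirin antiplatelet nor their adherence to it. The missing row tends to overstate adherence, but the net direction is not established while rows cannot be marked as not prescribed. The conclusion assumes that the annex grid is the form used and that drugs are not added by hand. It concerns measurement only, not which drugs are prescribed. The point is worth acting on because the repair before interviews is small and the lost ratings cannot be fully recovered afterwards.

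**What to change.** **Before or during data collection.** In MYMEDS Section 6 of the proforma:

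- add a row 'Other antiplatelet (specify)' below aspirin;
- add a 'Not prescribed' column;
- state in 7.10 that the any-SPM rule applies to all prescribed rows and only to those;
- report antiplatelet adherence from the two antiplatelet rows together.

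**If interviews are complete** (section 16 places them in December 2024 to June 2025):

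- label the row as aspirin adherence;
- use the medical record review planned in 7.9 to report how many participants were on a non-aspirin antiplatelet;
- state that adherence to those drugs was not rated.

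Do not state that the overall proportion can only be biased upward.

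Do not try to recover hidden cases from items 3c ("I sometimes alter my medicines by cutting back or stopping taking them") and 5a (sometimes forgetting "to take my heart medicines"). Neither names a drug or refers to the past month. Reclassifying on them only in patients with a non-aspirin antiplatelet would make misclassification depend on regimen and could create a spurious association with pill burden, a listed independent variable.

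**Cost.** One row, one column and one sentence. The form becomes slightly longer and departs a little from the instrument's layout. After the interviews, the cost is a relabelled result, one count from the records and one stated limitation.
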